## 5.9 Exposure to Study Drug and Treatment Compliance

Extent of exposure (number of days of exposure to study drug), treatment compliance between each scheduled visits and overall compliance will be presented by actual treatment group for the Completer Analysis Set.

Additionally, treatment compliance will be summarized by the following categories:

- <80%
- Within 80-120%
- >120%

All data will be listed.

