### 5.1.4 Safety Analysis Sets

The Safety Analysis Set for the double-blind treatment phase will include all subjects who receive at least one dose of study drug.

The Safety Analysis Set for the open-label extension phase will include all subjects who received at least one dose of study drug, completed the double-blind treatment phase, and continued into the open-label extension phase. These subjects will be analyzed according to the actual study treatment received. The Safety Analysis Set will be used for analysis of safety endpoints. For outputs corresponding to each treatment phase, the analysis set defined for that corresponding phase will be used.

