### 5.1.5 Completer Analysis Set

The Completer Analysis Set for double-blind treatment phase will include all subjects in Safety Analysis Set who have Week 16 CDR-SB score.

The Completer Analysis Set for the open-label extension phase will include all subjects in double-blind treatment phase completer analysis set, who completed the double-blind treatment phase, and continued into the open-label extension phase. These subjects will be analyzed according to the actual study treatment received. The Completer Analysis Set will be used for summarizing treatment exposure and compliance.

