### 5.2.10 Treatment Compliance

Treatment compliance will be calculated per visit as follows:

$$\frac{\text{Total number of capsules dispensed at Visit X} - \text{Total number of capsules returned at Visit Y}}{[\text{Date returned (Visit Y)} - \text{Date dispensed(Visit X)}] \times 3} \times 100$$

Period	Visit Interval	Visit X	Visit Y
Double-Blind Treatment Phase	Baseline to Week 2	Baseline	Week 2
	Week 2 to Week 4	Week 2	Week 4
	Week 4 to Week 8	Week 4	Week 8
	Week 8 to Week 12	Week 8	Week 12
	Week 12 to Week 16	Week 12	Week 16
Open-Label Extension Phase	Week 4 to Week 8	Week 4	Week 8
	Week 8 to Week 16	Week 8	Week 16
	Week 16 to Week 32	Week 16	Week 32

Overall compliance will be calculated as:

$$\frac{\text{Total number of capsules dispensed} - \text{Total number of capsules returned}}{[\text{Date of last dose} - \text{Date of first dose}] \times 3} \times 100$$

Any kits that are not returned will be considered missing data and corresponding treatment compliance will not be calculated.

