## 5.12 Safety Analyses

The safety analyses will be presented by the treatment received for the Safety Analysis Set for each treatment phase.

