**Confidentiality Statement**

This document is the property of Worldwide Clinical Trials Inc. and may not be duplicated, copied, altered or removed from company without prior approval from Worldwide Quality Assurance or in compliance with Worldwide Standard Operating Procedures.

Worldwide Clinical Trials Controlled Quality Management Document			
 WORLDWIDE <small>CLINICAL TRIALS</small>	Sponsor:	EIP Pharma, Inc.	
	Protocol Number:	EIP21-NFD-504	
STATISTICAL ANALYSIS PLAN			

Table Number	Table Title	Validation Method	Shell Number (if repeat)	Topline
	Relationship, Open-Label Extension Phase - Safety Analysis Set			
14.3.1.7a	Treatment-Emergent Adverse Events Leading to Early Withdrawal by System Organ Class, Preferred Term, Double-Blind Treatment Phase - Safety Analysis Set	IP		
14.3.1.7b	Treatment-Emergent Adverse Events Leading to Early Withdrawal by System Organ Class, Preferred Term, Open-Label Extension Phase - Safety Analysis Set	IP	14.3.1.7a	
14.3.2	Listings of Deaths, Other Serious and Significant Adverse Events			
14.3.2.1	Serious Treatment Emergent Adverse Events - Safety Analysis Set	IP		Topline
14.3.2.2	Deaths - Safety Analysis Set	IP		
14.3.3	Narratives of Deaths, Other Serious and Certain Other Significant Adverse Events			
14.3.4	Abnormal Laboratory Values			
14.3.4.1	Abnormal Laboratory Values – Safety Analysis Set	IP		
14.3.5	Extent of Exposure, Dosage Information, And Compliance			
14.3.5.1a	Exposure to Study Drug and Treatment Compliance, Double-Blind Treatment Phase - Completer Analysis Set	IP		
14.3.5.1b	Exposure to Study Drug and Treatment Compliance, Open-Label Extension Phase - Completer Analysis Set	IP	14.3.5.1a	
14.3.6	Vital Signs and Physical Examination			
14.3.6.1a	Vital Signs – Double-Blind Treatment Phase - Safety Analysis Set	IP		
14.3.6.1b	Vital Signs – Open-Label Extension Phase - Safety Analysis Set	IP	14.3.6.1a	
14.3.6.2a	Physical Examination – Double-Blind Treatment Phase - Safety Analysis Set	IP		
14.3.6.2b	Physical Examination – Open-Label Extension Phase - Safety Analysis Set	IP	14.3.6.2a	
14.3.6.3a	Shift Table of Physical Examination – Double-Blind Treatment Phase - Safety Analysis Set	IP		

QMD Ref: Worldwide-TMP-ST-054-1.0_Effective: 12Aug2022	Governing QMD: Worldwide-SOP-ST-026
Confidentiality Statement	

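### Double-blind exposure and compliance are reported only for subjects with a Week 16 CDR-SB, which drops most early stoppers and overstates mean days on drug relative to the safety population

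*SAP*

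**What the plan says.** - **Population for exposure and compliance.** Section 5.1.5 assigns the set: "The Completer Analysis Set will be used for summarizing treatment exposure and compliance". Section 5.9 repeats this: "overall compliance will be presented by actual treatment group for the Completer Analysis Set".
- **Who is in it.** Section 5.1.5: "The Completer Analysis Set for double-blind treatment phase will include all subjects in Safety Analysis Set who have Week 16 CDR-SB score". For the open-label extension, a subject must belong to this double-blind set, have completed the double-blind phase and have continued into the extension.
- **Outputs.** In Section 10, Table 14.3.5.1a is titled "Exposure to Study Drug and Treatment Compliance, Double-Blind Treatment Phase - Completer Analysis Set". Table 14.3.5.1b is its open-label counterpart. Listings 16.2.5.1 (exposure) and 16.2.5.2 (drug accountability) are also on the Completer Analysis Set. No exposure or compliance output on the Safety Analysis Set is listed, although Section 5.9 ends by promising that all data will be listed.
- **Population for safety.** Section 5.1.4: "The Safety Analysis Set for the double-blind treatment phase will include all subjects who receive at least one dose of study drug". Section 5.12: "The safety analyses will be presented by the treatment received for the Safety Analysis Set for each treatment phase".
- **Formulas.** Section 5.2.9 counts exposure as last dose minus first dose plus 1, less interruptions. Section 5.2.10 divides overall compliance by (last dose minus first dose) × 3, without the plus 1.
- **Addendum.** The post-lock addendum adds Section 5.2.9.1, a rule for a missing last-dose date, but leaves the population unchanged.

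**The concern.** Exposure tables tell the reader how long the subjects counted in the adverse event tables were on drug. Here the two sets of tables describe different people, and the difference is not random: having a Week 16 CDR-SB is closely tied to staying in the trial. Subjects who withdrew for an adverse event appear in the safety tables, but most of their days on drug appear nowhere. If early stopping differs between arms, the completer summaries will largely fail to show the resulting difference in exposure.

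Compliance matters for a second reason. The estimand in Section 2.3 names poor adherence as an intercurrent event and assumes such events are balanced across arms. Compliance by arm is the natural check of that assumption, and the check is weakened when most early stoppers are left out.

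**Working it through.** The SAP states no exposure figure to reproduce, so this is an illustration built on its planning values.

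**Inputs**
- 80 subjects per arm and 10% dropout (Section 3).
- 16 weeks of treatment = 112 days (Section 1).
- Mean days on drug among stoppers, *m*: not in the SAP; assumed, range 14 to 84.
- Simplifications: subjects with a Week 16 CDR-SB have the full 112 days without interruption, and every dropout lacks a Week 16 CDR-SB.

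**Denominators.** Adverse events: 80 per arm. Exposure: 80 × 0.9 = 72 per arm. About 8 per arm, or 16 in total, are left out.

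**Mean exposure.** Safety Set mean = (1 − d) × 112 + d × m, against 112 in completers. At d = 0.10:

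| m (days, assumed) | Safety Set mean (days) | Overstatement (days) | Overstatement (%) |
|---|---|---|---|
| 14 | 100.8 + 1.4 = 102.2 | 9.8 | 9.6 |
| 28 | 100.8 + 2.8 = 103.6 | 8.4 | 8.1 |
| 56 | 100.8 + 5.6 = 106.4 | 5.6 | 5.3 |
| 84 | 100.8 + 8.4 = 109.2 | 2.8 | 2.6 |

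Varying dropout from 5% to 20% over the same values of m gives 1.4 to 19.6 days (1.3% to 21.2%).

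**Total person-days** go the other way. At 10% dropout and m = 56, completers contribute 72 × 112 = 8064 per arm and the Safety Set 80 × 106.4 = 8512. The table omits 8 × 56 = 448.

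**Unequal dropout.** With 15% in one arm and 5% in the other, and m = 56 in both, the Safety Set means are 0.85 × 112 + 0.15 × 56 = 103.6 and 0.95 × 112 + 0.05 × 56 = 109.2 days. Under the same simplifications, the completer table shows 112 in both arms and the 5.6-day difference is lost.

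**Overall compliance formula.** A subject who takes every capsule for D days uses 3D capsules, so Section 5.2.10 returns 3D / [3(D − 1)]:
- D = 112: 336/333 = 100.9%.
- D = 30: 90/87 = 103.4%.
- D = 5: 15/12 = 125%, in the above-120% category of Section 5.9.
- D = 1: denominator zero, no value.

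The error is small for a full course but grows as exposure shortens. It must therefore be corrected together with the population.

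**The case against.** Several stronger readings are tempting, and the document does not support them.

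- **That every early stopper is left out.** The set depends on a Week 16 CDR-SB, not on finishing drug. A subject who stopped drug but attended Week 16 stays in. Table 1 in Section 5.2.4 maps an early-withdrawal CDR-SB on Days 90 to 117 to Week 16, and the SAP does not say whether a mapped value qualifies. Conversely, a subject who took every dose but missed that assessment is excluded. The correct word is most.
- **That compliance is biased upward.** Section 5.2.10 divides by each subject's own dosing window, so stopping early does not in itself lower the figure. With the day missing, it slightly raises it. Kits not returned yield no value. No direction can be claimed.
- **That the open-label table has the same fault.** The open-label completer set requires entry to the extension, not completion of it, so open-label stoppers are included. Table 14.3.5.1b loses only subjects who entered the extension without a Week 16 CDR-SB.
- **That all exposure is overstated.** This holds for mean days on drug. Total person-days is understated.

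The best defence is that early stopping is visible elsewhere: disposition with reasons for early termination, visit attendance, and adverse events leading to withdrawal, all by arm. That is true, but none of these gives days on drug or compliance. It is also true that adverse events are reported as numbers and percentages of subjects, that no exposure-adjusted rate is planned, and that compliance enters no efficacy model. This limits the consequence but does not make the exposure table right for its purpose. Nor does the promise in Section 5.9 to list all data help, since both relevant listings carry the completer restriction in their titles.

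**Conclusion.** The point holds for the double-blind phase. Sections 5.1.5 and 5.9, Table 14.3.5.1a and Listings 16.2.5.1 and 16.2.5.2 condition exposure and compliance on a post-randomisation assessment, while the safety tables cover everyone dosed. At 10% dropout, mean days on drug is overstated by about 3 to 10 days (2.6% to 9.6%). This rests on the assumed 14 to 84 days among stoppers, full exposure in completers, and a dropout rate that is a sample-size assumption rather than an observed value. For compliance, the established defects are the missing subjects and the missing day in the formula. This is a reporting defect that should be corrected. It does not touch the primary analysis, any hypothesis test or any adverse event count.

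**What to change.** 1. In Sections 5.1.5 and 5.9, Tables 14.3.5.1a and 14.3.5.1b, and Listings 16.2.5.1 and 16.2.5.2, replace the Completer Analysis Set with the Safety Analysis Set of the corresponding phase. Keep completers as an optional extra row in the tables. The change to 14.3.5.1b matters little but keeps the phases consistent.
2. In Section 5.2.10, use (last dose − first dose + 1) × 3 as the overall compliance denominator, consistent with Section 5.2.9. Full use then gives 336/336 = 100% over 112 days and 15/15 = 100% over 5 days.
3. If the completer row is kept, state in Section 5.1.5 whether an early-withdrawal CDR-SB mapped to Week 16 qualifies a subject as a completer.

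The cost is a change of population flag, one formula and a rerun of two tables and two listings. Dosing dates and capsule counts are already inputs to the planned formulas, and the addendum's rule covers a missing last-dose date, so no new data are needed. As the database is locked and the study unblinded, the change belongs in a further post-lock addendum. These outputs are descriptive, so making it now affects no inference.

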## 5.10 Efficacy Analyses

### 5.10.1 General Statistical Methodology

Efficacy data will be tabulated by treatment group and by visit for double-blind treatment and open-label extension phase separately. When tabulated, data will be presented using descriptive statistics for both observed values and as change from baseline. Continuous data will be summarized with the following descriptive statistics unless otherwise noted: number of observations, mean, standard deviation, median, minimum, and maximum; and 95% CI, as appropriate. Categorical data will be summarized with frequencies and percentages.

All statistical tests will be performed using a two-tailed 5% overall significance level, unless otherwise stated. All comparisons between treatments will be reported with 95% confidence intervals for the difference.

### 5.10.2 Primary Efficacy Endpoint (CDR-SB)

The primary efficacy endpoint is the change in CDR-SB in neflamapimod-treated subjects compared to placebo-recipients. The analysis for the primary endpoint will be performed using the mITT Analysis Set.

QMD Ref: Worldwide-TMP-ST-054-1.0 Effective: 12Aug2022	Governing QMD: Worldwide-SOP-ST-026
Confidentiality Statement	
This document is the property of Worldwide Clinical Trials Inc. and may not be duplicated, copied, altered or removed from company without prior approval from Worldwide Quality Assurance or in compliance with Worldwide Standard Operating Procedures.	

Worldwide Clinical Trials Controlled Quality Management Document		
 WORLDWIDE CLINICAL TRIALS	Sponsor:	EIP Pharma, Inc.
	Protocol Number:	EIP21-NFD-504
STATISTICAL ANALYSIS PLAN		

### 5.10.2.1 Primary Analysis

The difference between neflamapimod and placebo in the average change from baseline in CDR-SB score during the double-blind treatment phase (i.e., utilizing data from week 8, 12 and 16 in the model) will be estimated using a linear mixed effects model including treatment, time (in weeks), treatment-by-time interaction as fixed effects, cholinesterase inhibitor therapy (Yes/No), age, sex and baseline value as covariates. The random effect is on the subject term. An unstructured covariance structure will be used to model the within-subject error and an adjustment to the degrees of freedom will be made using the Kenward-Roger's approximation. If this model does not converge then the following covariance matrices will be used in order until the model converges: Toeplitz, first-order autoregressive, compound symmetry.

The estimate of the difference between neflamapimod versus placebo and standard error (SE) for the average change from baseline in CDR-SB will be derived from this LME model. The LS means, corresponding SEs, and 2-sided 95% CI for each treatment group, the treatment difference of LS means, corresponding SEs, 2-sided 95% CI and 2-sided p-value will be presented.

Example SAS code:

```
proc mixed data= method = REML alpha=0.05;
  class <subject> <treatment> <cholinesterase inhibitor therapy> <sex>;
  model <change from baseline> = <treatment> < cholinesterase inhibitor therapy> <sex> <age>
< baseline value> <time in weeks><treatment>*<time in weeks> / ddfm=kr s;
  random <time in weeks> / subject=<subject> type=un;
  lsmeans <treatment> / cl diff;
run;
```

### 5.10.2.2 Sensitivity Analysis

A sensitivity analysis will be performed to assess the robustness of the primary analysis to deviations from the assumptions around missing data.

The change from Baseline in CDR-SB will be repeated based on the mITT Analysis Set. All missing data will be handled by Multiple Imputation (MI) under an assumption of missing not at random (MNAR). Details of MI and SAS codes are provided below.

The monotone and non-monotone missing data will be imputed using a pattern mixture model such as control-based imputation (i.e., placebo arm reference) with the following SAS code. This statistical model uses fully conditional specification (FCS) with a predictive mean matching method where missing values will be imputed with random value from set of k=5 (default in SAS) closest estimated value and MNAR statement in the below code indicates that imputation will be control-based i.e., placebo value will be used to impute missing data points in both treatment arms.

```
proc mi data =  n impute = 5 seed = 134 out = <dataset_mnar>
```

QMD Ref: Worldwide-TMP-ST-054-1.0_Effective: 12Aug2022	Governing QMD: Worldwide-SOP-ST-026
Confidentiality Statement	
This document is the property of Worldwide Clinical Trials Inc. and may not be duplicated, copied, altered or removed from company without prior approval from Worldwide Quality Assurance or in compliance with Worldwide Standard Operating Procedures.	

Worldwide Clinical Trials Controlled Quality Management Document		
 WORLDWIDE CLINICAL TRIALS	Sponsor:	EIP Pharma, Inc.
	Protocol Number:	EIP21-NFD-504
STATISTICAL ANALYSIS PLAN		

```

minimum = . 1 1 56 0 0 0 0 maximum = . 2 2 x 18 18 18 18 round = . 1;
class <treatment> ; /*X=Max age in the data; Min and Max should be updated for each
endpoint*/
var <cholinesterase inhibitor therapy> <sex> <age> <baseline value> Week_8 Week_12
Week_16;
fcs nbiter = 1000 regpmm(Week_8 Week_12 Week_16);
mnar model(Week_8 Week_12 Week_16/ modelobs =(<treatment> = 'Placebo'));
run;

```

where *<treatment>* = *Treatment groups (Neflamapimod(40mg TID)/Placebo)*

Change from baseline will be calculated for the imputed values. A Linear mixed effect model will then be fit for each imputed dataset as described in the previous section and following sample SAS code will be used to fit the model.

```

ods output lsmeans=lsmeans diff=diff solutionF=solution;
proc mixed data= method=REML alpha=0.05;
by _imputation_;
class <subject> <treatment> <cholinesterase inhibitor therapy><sex>;
model <change from baseline> = <treatment> < cholinesterase inhibitor therapy> <sex> <age>
<baseline value> <time in weeks><treatment>*<time in weeks> / ddfm=kr s;
random <time in weeks> / subject=<subject> type=un;
lsmeans <treatment> / cl diff;
run;

```

The results of the model from each imputed dataset will be pooled using Rubin's rule to obtain single treatment effect estimates. The difference between the neflamapimod treatment group and placebo with corresponding SE and the 2-sided 95% CI, p-value (2-sided) will be presented. The sample SAS code given below will be used:

```

proc mianalyze data=;
by trt01pn;
modeleffects Estimate;
stderr StdErr;
ods output parameterestimates=<output>;
run;

```

### 5.10.2.3 Subgroup Analysis

The change from baseline in CDR-SB will be analyzed in for each subgroup of cholinesterase inhibitor therapy (Yes / No) separately, using similar methods as described in Section [5.10.2.1](#) except cholinesterase inhibitor therapy covariate will be removed from the model.

QMD Ref: Worldwide-TMP-ST-054-1.0 Effective: 12Aug2022	Governing QMD: Worldwide-SOP-ST-026
Confidentiality Statement	

This document is the property of Worldwide Clinical Trials Inc. and may not be duplicated, copied, altered or removed from company without prior approval from Worldwide Quality Assurance or in compliance with Worldwide Standard Operating Procedures.

Worldwide Clinical Trials Controlled Quality Management Document		
 WORLDWIDE CLINICAL TRIALS	Sponsor:	EIP Pharma, Inc.
	Protocol Number:	EIP21-NFD-504
STATISTICAL ANALYSIS PLAN		

## 5.10.3 Secondary Endpoints

### 5.10.3.1 *Change in TUG in neflamapimod-treated subjects compared to placebo-recipients*

Change in TUG will be analyzed in a manner similar to that of the primary endpoint as described in Section [5.10.2.1](#). The dependent variable is change from baseline in TUG. The analysis will be repeated for each subgroup of cholinesterase inhibitor therapy (Yes/No) separately, as described in Section [5.10.2.1](#) except cholinesterase inhibitor therapy covariate will be removed from the model.

### 5.10.3.2 *Change in the composite score of the Neuropsychological Test Battery (NTB)*

Change in NTB composite score defined in *Table 3* will be analyzed in a manner similar to that used for the primary endpoint as described in section [5.10.2.1](#). Change from baseline will be the dependent variable. The analysis will be repeated for each subgroup of cholinesterase inhibitor therapy (Yes/No) separately, as described in Section [5.10.2.1](#) except cholinesterase inhibitor therapy covariate will be removed from the model.

### 5.10.3.3 *ADCS-CGIC at Week 16 in neflamapimod-treated subjects compared to placebo-recipients*

ADCS-CGIC at Week 16 in neflamapimod vs. placebo will be compared utilizing a two-sided Mann Whitney U test (Wilcoxon Rank Sum Test).

The number of observations in each group, sum of ranks, mean, standard deviation, z-score and corresponding 2-sided p-value will be presented.

```
proc npar1way data= wilcoxon;
  class <treatment>;
  var < ADCS-CGIC at Week 16>;
  ods output WilcoxonScores=scores WilcoxonTest=Wilcoxon;
run;
```

The analysis will be repeated for each subgroup of cholinesterase inhibitor therapy (Yes/No) separately.

## 5.10.4 Exploratory Endpoints

Exploratory endpoints will not be tested for significance, but presented with treatment effect vs. placebo, with 95% confidence intervals.

QMD Ref: Worldwide-TMP-ST-054-1.0 Effective: 12Aug2022	Governing QMD: Worldwide-SOP-ST-026
Confidentiality Statement	
This document is the property of Worldwide Clinical Trials Inc. and may not be duplicated, copied, altered or removed from company without prior approval from Worldwide Quality Assurance or in compliance with Worldwide Standard Operating Procedures.	

Worldwide Clinical Trials Controlled Quality Management Document		
 WORLDWIDE CLINICAL TRIALS	Sponsor:	EIP Pharma, Inc.
	Protocol Number:	EIP21-NFD-504
STATISTICAL ANALYSIS PLAN		

#### **5.10.4.1 Change in the attention composite score**

Change in attention composite score defined in *Table 3* will be analyzed in a manner similar to that used for the primary endpoint as described in section [5.10.2.1](#). Change from baseline will be the dependent variable.

#### **5.10.4.2 Change in Dementia Cognitive Fluctuations Scale (DCFS)**

Change in DCFS will be analyzed similar to primary endpoint as described in Section [5.10.2.1](#). Observed results will be the dependent variable. Difference between the neflamapimod treatment group and placebo with corresponding SE and 2-sided 95% CI will be presented.

All DCFS data will be listed.

